### Activity Log

August 21, 2019: Reviewed by [name]  
August 23, 2019: Updated by [name]  
August 27, 2019: Reviewed by [name], [name], [name]  
August 30, 2019: Updated by [name]  
September 04, 2019: Reviewed by [name]  
September 05, 2019: Checklist filled in by [name]  
September 09, 2019: Randomization procedure updated by [name] using information from [name]  
October 11, 2019: Hypothesis testing procedures updated by [name]  
October 22, 2019: Reviewed by [name]  
October 23, 2019: Reviewed by [name]

---

## 1 Study Overview

In response to the high cost of artemisinin-combination therapy (ACT), publicly-funded, retail-sector ACT subsidies were adopted in many malaria-endemic countries. Declining prices of ACTs create a trade-off between access and targeting; lower prices improve uptake of effective therapies by those with malaria but also increase inappropriate use by those without malaria. Curbing inappropriate use and targeting ACTs to malaria cases requires parasitological diagnosis which is virtually absent in the retail sector. It is estimated that at least two thirds of ACTs purchased over-the-counter are consumed by individuals without malaria. Inappropriate use leads to wastage of public funds and prime conditions for the spread of drug resistant parasites, which could dramatically increase global mortality from malaria. Targeting subsidized ACTs to individuals with parasitologically-confirmed malaria would significantly contribute to the sustainability and cost-effectiveness of retail subsidies as well as safeguard the future efficacy of these key drugs. We propose an innovative conditional subsidy approach that links the ACT subsidy to the results of

a rapid diagnostic test (RDT), allowing the subsidy to be targeted only to parasitologically-confirmed malaria cases. This price differential makes information from a test more valuable and could drive appropriate consumption while reducing costs.

This study will be an individually-randomized 2X2 factorial trial and clients will be allocated, in equal proportions, to one of four treatment arms (210 individuals per arm). Each of the four treatment arms combines two factors, each of which have two levels, hence the choice of a 2x2 factorial design. Those two factors are:

1. An offer of a malaria RDT offered at one of two price levels-USD \$0.40 (0% subsidy) or USD \$0.20 (50% subsidy)
2. An offer of a discounted ACT conditional on a positive test result at one of two price levels- USD \$0.40 (67% subsidy) or USD \$0.00 (100% subsidy).

The intervention is designed to ensure fixed price point for consumers. Individuals who choose not to be tested for malaria, or who test negative for malaria, may purchase an ACT at the unsubsidized price of approximately USD \$1.20. Note that when referring to the two factors in the text below, we will use the terms “RDT subsidy intervention” and “conditional ACT subsidy intervention”.

## **1.1 Study Aims**

The goal of this study is to identify the combination of testing subsidies and conditional ACT subsidies that maximizes uptake of testing within specific budget constraints. Several studies, including our own, have shown that uptake of testing and ACT treatment are both sensitive to price. However, very little is known about how these prices should be related in order to maximize appropriate behavior and what effect conditional subsidies may have on treatment decisions. We will use an individually-randomized experiment to determine how different combinations of subsidies, allocated between testing and treatment, affect the decision to be tested for malaria before treatment among clients seeking care in the retail sector.

## **1.2 Study Hypotheses**

### **1.2.1 Primary Hypotheses**

RDT uptake (i.e. the proportion of clients who are tested with an RDT) will increase when the price of the RDT is reduced from \$0.40 (0% subsidy) to \$0.20 (a 50% subsidy), averaged over the ACT price levels.

RDT uptake will increase when the price of the ACT conditional on a positive test is reduced from \$0.40 to \$0 (67% subsidy vs 100% subsidy), averaged over the RDT price levels.

### **1.2.2 Descriptive Analysis**

Adherence to RDT test results consists of ACT purchasing behaviors among the untested, test negative, and test positive participants. Descriptive statistics of adherence conditional on the ACT price levels (67% subsidy vs 100% subsidy) will be generated to look for possible patterns of ACT purchasing behaviors in different scenarios. We will also assess the effect of seriousness of disease and duration of symptoms on adherence to RDT test results as a sub-analysis.

## **2 Study Population**

The study population will be any individual coming to a participating medicine retail outlet to purchase medicine for an acute, malaria like illness. Ten randomly selected retail medicine outlets in western Kenya will be selected for recruitment, which will happen on random days of the month to avoid individuals seeking to be recruited.

840 participants across 10 drug retail outlets in the study area will be recruited and randomly assigned in equal numbers to each of four arms using secret scratch cards. Children are eligible to participate if they are present with a parent or guardian. Inclusion of children ensures that we get a comprehensive picture of malaria infection and treatment decisions across all age groups. Children are at higher risk of malaria infection and disease which increases their importance to the study. They will also benefit from the opportunity to receive diagnostic testing immediately at the retail outlet, and they, along with their parent or guardian, can use the test results in deciding what drugs to purchase or other treatment actions to take. We will attempt to recruit all eligible participants who attend the outlet on a recruitment day. This will ensure that our sample is representative of the population seeking care in retail outlets in terms of age, gender and ethnicity. We do not have targets for recruitment based on gender, age or ethnicity.

### **2.1 Inclusion Criteria**

- Participants with fever or history of fever or malaria like illness
- Individual with malaria-like illness must be present at recruitment
- Older than one year of age

### **2.2 Exclusion Criteria**

- Any individual with signs of severe illness requiring immediate referral
- Individuals who have taken an antimalarial in the last seven days, including for the current illness
- Individuals who already have a prescription from a facility or medical provider, regardless of whether they have documentation of a test
- Pregnant women will be enrolled and offered an RDT, but will be advised to seek treatment through a health care provider.

### **2.3 Randomization Procedure**

Each client who consents to be part of the study will receive a scratch card that will indicate their intervention arm (i.e. the combination of prices at which they will be offered an RDT and a conditional ACT). We will stratify on retail outlet to ensure that each of the 10 outlets has a similar number of clients who are assigned to the four study arms (approximately 21 per arm, per retail outlet for a total sample of 210 per arm). Due to the nature of the interventions, it is not possible to blind participants and research assistants to the allocation received. Study statisticians will be blinded during the analysis phase. Scratch cards were allocated in batches of 100 or 60 (25 of each or 15 of each arm) and shuffled thoroughly. Batches were assigned to specific outlets based on sales volume (i.e., higher-volume outlets received larger batches of 100 cards, smaller outlets received batches of 60 shuffled cards). Participants were asked to select a card from the shuffled stack. Cards were replenished when ten were remaining.

### **2.4 Sample Size Justification**

Our sample size calculations are based on the expected changes in testing uptake with each of the price changes for the two commodities (RDT and ACT). We expect that reducing the price of the RDT from \$0.40 USD to \$0.20 will increase the percentage of clients who choose to get tested by 15 percentage points. We also expect that reducing the ACT price, conditional on a positive test result, from \$0.40 to \$0.00 will increase the uptake of testing by 10 percentage points (see Table 1, which is a copy of Table 2 in the Research Strategy).

As is commonly done for 2X2 factorial trials that seek to separately test for main effects of each of the two factors, our study is powered to detect the effects of the price reductions of each commodity (RDT and ACT) independent of the price of the other commodity. That is, for the purposes of our power calculations we assume no statistical interaction between the two commodities because our previous evidence suggests that any interaction effects between the prices in the two commodities are likely to be small and therefore not large enough in terms of public health importance to choose to power on such interactions [1]. That is, while we expect the uptake of testing to be sensitive to the price of both the RDT and the ACT, we do not expect that price changes in one commodity will have a different effect on testing uptake depending on the price of the other commodity.

ACT Price to client if he/she tests positive for malaria (Price for RDT negative or untested client = \$1.20)	RDT Price to client		Overall Proportion Tested*
	I. \$0.20 USD (50% subsidy)	II. \$0.40 USD (No Subsidy)	
I. \$0 USD (100% subsidy)	85%	70%	77.5%
II. \$0.10-0.40 USD (67% subsidy)	75%	60%	67.5%
Overall Proportion Tested*	80%	65%	

\* Assuming the same sample size in each of the 4 study arms

**Table 1:** Aim 1 2x2 factorial study design showing the four arms and the assumed level of testing in each arm. The 67% ACT subsidy-level was chosen to match the original AMFm prices in Kenya. We do not test the non-subsidized ACT price because our aim is to identify an ACT discount level that can incentivize individuals to get tested for malaria. Input from policy-makers suggests that fully-subsidized, free RDTs may not be acceptable from a programmatic standpoint ([name], *pers. comm.*). Therefore, we do not include a 100% RDT-subsidy level.

\* Assuming the same sample size in each of the 4 study arms

\*\* At current market prices, this subsidy level gives the following prices to the consumer: 6 tablets@\$0.10; 12 tablets@\$0.15; 18 tablets@\$0.20; 24 tablets@\$0.40.

Using a standard approach based on a two-sample Z-test for a comparison of proportions for each of the two main effects at a two-tailed 5% Type 1 error rate (alpha), our sample size should provide 90% power to detect each of our two comparisons of interest (i.e. two main effects). To determine the overall sample size of the study, we calculated the sample size needed for each of the two main comparisons of interest, and chose the larger overall sample required (see Table 2). Specifically, because we estimated that we needed a total sample size of 838 participants (i.e. of 418 participants at each of the two conditional ACT price levels) to test for the main effect of the conditional ACT subsidy price levels compared to a total sample size of 374 (i.e. of 187 at each of the two RDT price levels) to test for the main effect of the RDT price levels, we therefore needed to plan the study by using the more restrictive sample size in order to be able to address both study goals. Given that the trial will be conducted within 10 drug retail outlets, there could be clustering of outcomes due to some participants being enrolled from the same shops. Based on our ongoing work in the region, we expect such clustering to be minimal with an intra-class correlation coefficient of at most 0.008. Even with this level of clustering, we would still have at least 80% power to detect our expected effect sizes.

Although a priori we do not anticipate a significant interaction effect, we will perform an additional test to evaluate that assumption. If, as expected, a significant interaction effect is not detected, we will perform our planned tests of the main effects of each of the factors (see the first column in Table 2). Thus, we will have conducted three total significance tests, and will adjust for familywise Type 1 error rate using the Bonferroni correction ( $\alpha=0.05/3=0.0167$ ). As shown in the last column of Table 2, we would still have 80% power to detect the expected effect sizes with the total sample size of 838, given that Bonferroni correction is a conservative method of familywise error rate adjustment. We will use different error rate allocation methods to gain more power in statistical analysis. In the unlikely case that a significant interaction effect exists, we will instead test the conditional effects of each of factor and adjust for Type I error accordingly (as described in section 4.2; see Table 3).

**Table 2:** Expected effect sizes for the main comparisons of interest and sample size required for 80%,

Description of Comparison	Expected Increase in Testing Uptake	Total sample size required for 90% power ( $\alpha=0.05$ )	Total sample size required for 85% power ( $\alpha=0.0167$ )	Total sample size required for 80% power ( $\alpha=0.0167$ )
Effect of reducing conditional ACT price from \$0.40 (67% subsidy) to \$0.00 (100% subsidy)	10 percentage points (from 67.5% to 77.5%)	838	936	832
Effect of reducing RDT price from \$0.40 (no subsidy) to \$0.20 (50% subsidy)	15 percentage points (from 65% to 80%)	374	414	370

85%, and 90% power to detect those effect sizes (with two-tailed Type 1 error set at 0.0167 and 0.05, and using standard methods for two-sample comparison of proportions).

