In the primary model (Model 1),  $\beta_0$  represents the overall mean of log-mean level (i.e. log-proportion) of testing uptake across all treatment arms.  $\beta_1$  represents the deviation of the log-proportion of testing uptake from the overall mean when reducing the price of the RDT from \$0.40 to \$0.20, averaged across ACT subsidy levels, while  $\beta_2$  represents the deviation of the log-proportion of testing uptake from the overall mean when reducing the price of the ACT, conditional on a positive test, from \$0.40 to \$0, averaged across RDT subsidy levels.  $\beta_3$  represents the interaction effect between the two price changes: it is the additional effect on log-proportion of testing uptake when both commodities are offered at the lower price level or higher price level, and also the negative additional effect if only one of RDT and ACT is offered at a lower price level. Relative risk ratio for the average effect of each of the price reductions cannot be obtained due to the nature of the model. However, an approximation of it can be obtained by exponentiating the parameters and deriving corresponding 95% confidence intervals.

In the secondary model (Model 2),  $\beta_0$  represents the overall mean of the proportion of testing uptake across all treatment arms.  $\beta_1$  represents the deviation of the proportion of testing uptake from the overall mean when reducing the price of the RDT from \$0.40 to \$0.20, averaged across ACT subsidy levels, while  $\beta_2$  represents the deviation of the proportion of testing uptake from the overall mean when reducing the price of the ACT, conditional on a positive test, from \$0.40 to \$0, averaged across RDT subsidy levels.  $\beta_3$  represents the interaction effect between the two price changes: it is the additional effect on the proportion of testing uptake when both commodities are offered at the lower price level or higher price level, and also the negative additional effect if only one of RDT and ACT is offered at a lower price level. Absolute risk differences and corresponding 95% confidence intervals can be obtained by directly evaluating the model parameters.

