Our two primary goals are to determine whether RDT uptake increases significantly when the price of the RDT is reduced from \$0.40 (no subsidy) to \$0.20 (a 50% subsidy), averaged over the ACT price levels (i.e. the main effect), and when the price of the ACT conditional on a positive test is reduced from \$0.40 to \$0 (67% subsidy vs 100% subsidy), averaged over the RDT price levels (i.e. the main effect). That is, we wish to test for the main effects of these two commodities. These can be evaluated by testing the null hypotheses  $H_0: 2\beta_1=0$  and  $H_0: 2\beta_2=0$ , with 2% Type 1 error rate respectively. Although, a priori, we hypothesized no statistical interaction

on absolute scale in our sample size calculations, a secondary aim is to determine whether the effect of each of the price changes depends on the price of the other commodity. This can be tested by evaluating the null hypothesis  $H_0: \beta_3=0$  in model 2 on the absolute scale with 1% Type 1 error rate. If this effect is statistically different from zero, we will report the effect of the price reductions of each commodity conditional on the price of the other commodity, with a Type 1 error rate of 1% respectively. If, however, as we expect, there is no statistically significant or scientifically meaningful interaction (i.e.  $\beta_3$  is close to zero), we will estimate the average effects from a model with interaction to match the study design with a Type 1 error rate of 2% respectively. The allocation of Type 1 error rate is based on the a priori importance of the hypothesis tests and provides more power than the conservative strategy employed in our sample size calculations (section 2.4). Contrasts of interest are summarized in Table 3.

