### **5.3 Level of Randomization**

In Aim 1, we randomize at the individual level because we are testing the effect of RDT and ACT prices on individual clients' decision about whether to get tested for malaria. For a given sample size of clients, randomizing at the individual level gives us greater statistical power for detecting effect sizes than randomizing at a higher level such as the retail outlet.

Since clients generally enter the shop one at a time, we do not expect there to be any spillovers between the treatment arms (i.e. we do not expect that offering a client one combination of subsidies will affect the decision-making of a client assigned to another treatment arm within the same shop). Moreover, since the study will be administered by the research assistant (and not the shopkeeper), this should minimize the concern that individual testing decisions might be influenced by the shopkeeper. Randomizing at the individual level also reduces the likelihood that clients will visit specific retail outlets in order to get the highest subsidy levels of the two commodities.

We do not expect there to be significant clustering of the outcome by retail outlet because the 10 retail outlets will be chosen to have similar characteristics in terms of location, size, client load, length of time the shop has been open, inventory, and qualifications of the drug shop owner. We will further minimize clustering by having a research assistant perform the RDT (rather than the shopkeeper), rotating the research assistants across the 10 outlets, and by ensuring that the intervention is delivered in a consistent manner across all outlets. Based on our ongoing work in the region, we expect at most an intra-class correlation coefficient of approximately 0.008, which would still give us 80% power to detect our expected effect sizes. Since we only have 10 shops (i.e. 10 clusters) we will need to use finite-sample correction methods to estimate parameter standard errors. Specifically, the Kauerman-Carroll approach is recommended when the number of individuals per unit is similar across all units [4, 5].

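### Power for the ACT subsidy effect is headlined at 90% (5% alpha), but the effect is tested at a fixed 2%, where power is about 82%; Holm within the same 4% gives about 88% with no extra participants

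*SAP*

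**What the plan says.** Protocol 7.2 and SAP 2.4 base the sample size on two-sample Z-tests at a two-tailed 5% level and state that "our sample size should provide 90% power to detect each of our two comparisons of interest". The ACT comparison (67.5% against 77.5% tested) needs the larger total, 838, and so sets the planned 840. The Protocol gives no other alpha.

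SAP 2.4 then counts three tests (the interaction and two main effects), applies Bonferroni at 0.0167, and says "we would still have 80% power to detect the expected effect sizes with the total sample size of 838". It adds that other allocations of the error rate will be used to gain power.

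SAP 4.2 and Table 3 set that allocation: 1% for the interaction, and each main effect "with 2% Type 1 error rate respectively". SAP 4.2 says this "provides more power than the conservative strategy employed in our sample size calculations", but gives no figure. Intervals are planned at the conventional level ("deriving corresponding 95% confidence intervals"; Table B3 has the same column).

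On clustering with an intra-class correlation of at most 0.008, Protocol 7.2 and SAP 2.4 say "Even with this level of clustering, we would still have at least 80% power to detect our expected effect sizes". SAP 5.3 repeats it: "which would still give us 80% power to detect our expected effect sizes". None of the three gives an alpha or a design effect.

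**The concern.** Power belongs to the test that will be run. A Protocol reader is told 90%, and a SAP reader is told 90% and then 80% at a level that is not used. Neither sees the power at 2%. This matters most for the ACT effect, because it determines N and has little to spare; the RDT effect has ample power at any of these levels.

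The SAP also says that the allocation was chosen to gain power. A fixed 2% for each main effect leaves alpha with the RDT test that it almost never needs and that the ACT test cannot use. Finally, a clustering assurance without its alpha cannot be carried over to a 2% test.

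**Working it through.** **Inputs.** ACT rates 67.5% and 77.5%; RDT rates 65% and 80%; cell rates 85, 70, 75 and 60% (SAP Tables 1 and 2). 210 per arm, so n = 420 per factor level (SAP section 1). Alphas 0.05, 0.0167 and 0.02 (SAP 2.4, 4.2, Table 3).

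**Reproducing the plan.** The pooled Z-test formula gives total N for ACT of 834 (90%, 0.05), 936 (85%, 0.0167) and 834 (80%, 0.05/3; 832 at 0.0167). SAP Table 2 has 838, 936 and 832. For RDT it gives 370, 414 and 370, against 374, 414 and 370. The method is therefore the documents' own.

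**ACT power.** Power = Φ[(0.10 − z·s0)/s1], with s0 = √(2 × 0.725 × 0.275/420) = 0.03081 and s1 = √((0.675 × 0.325 + 0.775 × 0.225)/420) = 0.03062.

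| alpha | z | ACT power | RDT power |
|---|---|---|---|
| 0.05 | 1.960 | 90.2% | 99.8% |
| 0.04 | 2.054 | 88.5% | 99.8% |
| 0.02 | 2.326 | 82.2% | 99.5% |
| 0.0167 | 2.394 | 80.4% | 99.4% |

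Reaching 90% for ACT at a fixed 0.02 would take 517 per level, N = 1,034.

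**Holm within 4%.** The smaller p-value is compared with 0.02; if that test rejects, the other is compared with 0.04. Treating the two tests as independent:
- ACT: 0.8225 + (0.8848 − 0.8225) × 0.9950 = 0.884.
- Both nulls rejected, fixed split: 0.8225 × 0.9950 = 0.818.
- Both nulls rejected, Holm: 0.8225 × 0.9978 + 0.0623 × 0.9950 = 0.883.

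Over the 80.4% at Bonferroni, the fixed split gains 1.8 points for ACT and Holm gains 8.0.

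**Planned log-link contrast.** 2β2 = 0.5 × [ln 0.85 + ln 0.70 − ln 0.75 − ln 0.60] = 0.1397 (risk ratio 1.15). SE = √(0.25 × Σ(1 − p)/(210p)) = 0.0437, so z = 3.195. Power is 89.2% at 0.05, 80.7% at 0.02 and 87.3% with Holm. RDT power at 0.02 is 99.3%.

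**Simulation** of the four cells (400,000 trials). Pooled Z-test: ACT 82.8% fixed, 88.9% Holm. Error control under Holm: with a true RDT effect and no ACT effect, ACT is falsely rejected in 3.9% of trials, or 4.9% counting the 1% interaction test. With all four arms equal, familywise error is 4.8–4.9%. The bound is 0.01 + 0.04 = 0.05.

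**Clustering.** Several design effects could lie behind the 80% figure:

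| Basis | Design effect | 0.05 | 0.02 |
|---|---|---|---|
| 84 per outlet: 1 + 83 × 0.008 | 1.664 | 71.2% | 57.6% |
| 42 per outlet per ACT level: 1 + 41 × 0.008 | 1.328 | 80.6% | 68.9% |
| Outlets differ only in overall uptake: 1 − 0.008 | 0.992 | 90.4% | 82.6% |

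The second row is the one that matches 80%, but that basis is inferred. If the ACT effect itself varied across the 10 outlets with an SD of 3 or 5 points (assumed values; SD²/10 added to the variance of the risk difference), power at 0.02 would be 78% or 71%, and 85% or 80% with Holm.

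**The case against.** Nothing is miscalculated: 90% is correct for the 5% level named in the same sentence, and a 2%+2% split chosen on prior importance is legitimate. The SAP also discloses a loss. It gives 80% at 0.0167, and since 0.02 is larger, 80% is a valid floor for the test to be run; without clustering that floor is not breached. For a SAP reader the missing information is thus about two points. All of this stands, and it limits the seriousness. It does not help a Protocol reader, who sees only 90%.

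Holm's 88% depends on the RDT test rejecting first. With RDT rates centred at 72.5%, the same formula gives ACT power of about 87% for a 10-point RDT effect, 86% for 7.5, 84% for 5 and 82% for none. The dependence is real and should be stated. Holm nevertheless rejects whatever the fixed split rejects, so it cannot lose power.

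The 69% figure uses a design effect that suits allocation by outlet, whereas clients are randomised individually within outlets. SAP 5.3 also describes similar outlets and rotating research assistants. The favourable case may well apply, so what is asked for is the basis of the claim, not its withdrawal.

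These calculations also leave out covariate adjustment, which SAP 5.5 expects to improve precision, and the small-sample correction. They are approximations to the planned test and should be labelled so.

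**Conclusion.** The point holds. At the 2% level the SAP will use, power for the ACT main effect is about 82% by the documents' own method (about 81% for the log-link contrast), against a headline of 90%, and neither document says so. The fixed split is valid but gives up about 6 points of ACT power that Holm recovers within the same 4%. These figures assume the rates in SAP Table 1, 420 analysed per level, no clustering and, for Holm, the 15-point RDT effect.

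The clustering assurance holds at 2% if subsidy effects do not vary by outlet. It does not hold on the one basis found to reproduce the stated 80%. This should be corrected, but it does not threaten the trial's validity or its error control.

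**What to change.** 1. **SAP 4.2 and Table 3.** Keep 1% for the interaction. Test contrasts 1a and 1b by Holm within their existing 4%: smaller p-value against 0.02 and, if rejected, the other against 0.04. Leave contrasts 2a–2d as they are. State that simple confidence intervals will not match the Holm decisions exactly, and label the 95% intervals as unadjusted; they already do not match 2% tests.
2. **Protocol 7.2 and SAP 2.4.** Report ACT power at the alpha actually used: about 82% at a fixed 2%, or about 88% with Holm given a 15-point RDT effect, labelled as a two-sample Z-test approximation.
3. **Protocol 7.2, SAP 2.4 and SAP 5.3.** Give the alpha, the design effect and the assumption about outlet-varying subsidy effects behind the 80% clustering figure.

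The cost is text, with no added participants; the headline ACT power falls from 90% to about 88%. Item 1 changes the primary decision rule, and the SAP already describes card allocation and data collection in the past tense. It therefore needs a dated amendment made while the statisticians are still blinded. If that point has passed, keep the fixed 2% and make items 2 and 3 only.
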